
Efficacy [If applicable]
	
Group 1: Multi-Layer Bandage
 
 
• Will be seen in clinic once per week for: 
 
○ Wound assessment
 
○ wound dressing changes, debridement, if necessary, as determined by the treating study investigator
 
○ wound tracing; photo
 
○ limb volume measurements
 
 
 
• Subjects will be instructed to wear the MLB 24 hours daily, except upon removal and re-application during weekly clinic visits with debridement as determined necessary by PI
 
 
Group 2: ACTitouch Adaptive Compression System
 
 
• Will be seen in the clinic at weeks 1, 2, 4, 6, 9, 12, 16 during the treatment period. Subjects who experience complete healing of the study VLU will return to the investigational site 1, 2 and 3 months post heal. 
 
○ wound assessment, as applicable
 
○ wound dressing changes, debridement, if necessary, as determined by the treating study investigator
 
○ wound tracing; photo, as applicable
 
○ limb volume measurements
 
 
 
• Subject will be instructed to wear the AT in sustained mode for a minimum of 12 hours per day plus 2 hours IPC mode.
 

Safety
	
Adverse event monitoring  Subject interview  Physical examination

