- Subject's target ulcer measures less than 1.5cm^2 at the Randomization Visit.
- Subject appears to have evidence of infection in any ulcer.
- The sum of the ulcer areas on the subject's study limb is > 50cm^2.

5.2.4 Subject Withdrawal or Early Termination:

Subjects will exit the study if they meet any of the following criteria:

- Subject death
- Subject voluntarily withdraws or investigator's decision
- Subject experiences an adverse event that in the investigator's clinical judgment necessitates study discontinuation
- Ulcer recurrence during the 3 month follow up period
- Subject acquires any of the exclusion criteria, except
  - If subject acquires an infection, they may be treated for the infection and continue in the trial in the investigator's discretion. The investigator can instruct the subject to cease sustained or IPC treatment for up to two (2) consecutive weeks but no more than four (4) weeks total. If the subject is required to abstain from study treatment for greater than the amount described above, the subject will be removed from the study.

5.3 Dosage:

Run-in

All subjects will participate in a two week run-in phase. The treatment will include multi-layer compression bandaging which must be worn 24 hours a day except during clinic visits. The run-in phase is intended to assess the subject's initial response to standard of care treatment using multi-layer bandaging before receiving treatment with the investigational device.

VLU Treatment Period

All subjects enrolled will be randomized into either treatment using the ACTitouch system or multi-layer bandaging which consists of either PROFORE or Coban 2.

Investigational Group: Subjects assigned to the ACTitouch system must wear the device in sustained mode during all wakeful hours (at least 12 hours each day) and IPC mode for a minimum of 2 hours each day. Subjects will be instructed to remove the ACTitouch for bathing and when driving or operating machinery, and reapply immediately after these activities.

At each visit the subject’s compliance will be evaluated via the compliance tracker on the ACTitouch device.

Subjects randomized to the ACTitouch arm of the study will also be contacted weekly between study visits by study personnel to support device compliance and answer questions as outlined in Section 7.16.

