**6.0 Study Visit Summaries:**

6.1 Screening Visit:

At this visit, the patient will be asked to provide written informed consent and inclusion and exclusion criteria will be evaluated to ensure that the patient meets all entrance criteria. See the Study Schedule of Activities section 7.17 for visit activities. After the informed consent process is complete, the subject will begin the run-in phase of the study.

Subjects may be enrolled if they are on a current Pentoxifylline regimen, but Investigators should not start patients on Pentoxifylline during the trial if the patient is not taking the drug at enrollment.

6.2 Run-in Visit:

There could be up to 4 visits during the run in phase, 3 visits if the Screening and Baseline visits occur on the same day. The visit schedule is as follows Screening/Baseline; Run-in Week 1 and Randomization ( $\pm 2$  days). The subjects will follow the treatment regimen outlined in section 7.17. At each visit the study staff will access the ulcer. If the subject meets any of the exclusion criteria listed in section 5.2.3 at the Randomization Visit the subject will be excluded from the study.

6.3 Randomization Visit:

At the randomization visit the subject will undergo procedures as outlined in the Study Schedule of Activities table in section 7.17.

The subject will leave the randomization visit with:

- Schedule for the next study visit (if possible, follow-up visits should be scheduled at the same time of day)
- Instructions on use and application of the assigned study apparatus, as applicable
- Diary and instructions to record daily activity
- Contact information and instructions to call if any problems arise

6.4 Treatment Visits (Weeks 1-16 or healed):

Investigational Group: Subjects will be seen in clinic at weeks 1, 2, 4, 6, 9, 12, 16 ( $\pm 2$  days) for 16 weeks or until the VLU is completely healed, as defined by complete closure with no open area or exudate. At the visits the subject will undergo the procedures as outlined in the Study Schedule of Activities table in section 7.17.

Control Group: Subjects will complete weekly visits for 16 weeks or until the VLU is completely healed, as defined by above. At the weekly visits the subject will undergo procedures as outlined in the Study Schedule of Activities table in section 7.17.

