The study staff will review the subject diary with the subject during each visit to ensure that all entries are complete and understood by the study staff. Any corrections must be made by the subject, and initialed and dated by them.

6.5 Support Contact:

Subjects randomized to the ACTitouch arm of the study will be contacted by study personnel (via text or phone call). The first follow up contact will occur 3 days ( $\pm 1$  day) after the Randomization Visit and the second follow up contact will occur 3 days ( $\pm 1$  day) after the Treatment Week 1 Visit.

For the remainder of the VLU treatment period, follow up contact will occur on weeks that the subject is not returning to the clinic for a study visit. The subject will be contacted during treatment weeks 3, 5, 7, 8, 10, 11, 13, 14, and 15 ( $\pm 2$  days from optimal date). If an ACTitouch subject is seen for an unscheduled study visit

within one of these windows, this will take the place of the support contact for that week.

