**6.7 Unscheduled Study Visit:**

The subject may return to the investigational site for unscheduled visits during the study. At this unscheduled study visit the subject will complete all study procedures as outlined in the Study Schedule of Events Section 7.17.

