#### 7.7 Wound Debridement:

Ulcer debridement will be undertaken as needed per the investigator's clinical decision. The methods of debridement may include enzymatic, sharp, surgical, and mechanical debridement and/or pulse lavage.

7.8 Wound Dressings:  
All subjects will undergo wound dressing changes, either in the clinic or at home. Wound dressing will be selected by the investigator. Generally, “dry ulcers” will require hydrocolloid dressings and “wet ulcers” will require foam or alginate.

7.9 Wound Photograph and Tracing:  
At each study visit, (if applicable) the study ulcer will be photographed and the wound will be traced using the Silhouette™ system (Appendix E).

In addition, at the initial visits all ulcers on the study limb will be photographed and traced to ensure that the sum of the areas is not greater than 50cm^2. Any ulcers that form on the study limb during the course of the study will also be photographed and traced for AE documentation.

The initial visit, enrollment visit, and healed visit image and tracing will be evaluated by a single independent adjudicator to increase integrity and to provide a blinded analysis. Ulcer surface areas that fall on or near the minimum or maximum ulcer surface area allowed for study inclusion will be adjudicated in a timely manner. Study staff will have access to the adjudication results by a time no later than the next scheduled subject visit.

7.10 Tissue/Skin Assessment:  
The subject’s legs will be examined for irritation, trauma and ulceration at each study visit. At any time during the study the investigator may determine that a tissue/skin change requires the subject to be withdrawn from the study.

7.11 Compression Application:  
Application of ACTitouch System:  
The ACTitouch system will be applied by the trained study staff. First the ACTitouch under-sock will be applied. The sock will be in direct contact with the skin and wound dressings and the ACTitouch sleeve will wrap around the pre-covered leg. The ACTitouch will be applied while the subject is seated, with the feet lightly resting on the floor.

Application of Multi-Layer Bandaging:  
The trained study staff will apply the multi-layer bandaging according to manufacturer’s instructions. The multi-layer bandaging will be in direct contact with the skin and the wound dressings.

7.12 Application Timing:  

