8.2.3 Other Safety Analyses

The following analyses will be carried out on the Safety Populations. ACTitouch® treated subjects will be compared with multi-layer bandaging treated subjects in terms of:

- the difference in the incidence of ulcer-related adverse events (defined as ulcer infections, maceration, allergic reaction to dressing, or hospitalization for worsening VLU) at 16 weeks using the Cochrane-Mantel-Haenszel (CMH) test (Table 14.3.3).

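### The ulcer-related adverse event comparison makes no allowance for 16 scheduled limb examinations in control against 7 in ACTitouch, so short-lived events can be under-detected in the device arm

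*SAP*

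**What the plan says.** **Test.** SAP 8.2.3 compares "the difference in the incidence of ulcer-related adverse events (defined as ulcer infections, maceration, allergic reaction to dressing, or hospitalization for worsening VLU" by CMH, with week 16 as the time point. The note to Table 14.3.3 says that the test adjusts for ulcer size and duration. Protocol 12.6.5 names a Kruskal-Wallis test for the same incidences. Neither document adjusts for number of visits, time observed or how an event was found.

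**Visits (Protocol 6.4).** For ACTitouch: "Subjects will be seen in clinic at weeks 1, 2, 4, 6, 9, 12, 16". For control: "Subjects will complete weekly visits for 16 weeks or until the VLU is completely healed".

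**Examination (Protocol 7.10).** The subject's "legs will be examined for irritation, trauma and ulceration at each study visit". Protocol 7.6 likewise ties assessment of drainage and the periwound area to study visits.

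**Between visits.** ACTitouch subjects alone receive text or phone contacts, two early ones and then weekly: "The subject will be contacted during treatment weeks 3, 5, 7, 8, 10, 11, 13, 14, and 15" (Protocol 6.5). Protocol 5.3 gives their purpose as "to support device compliance and answer questions". Both arms have a diary reviewed at visits, instructions to call with problems, and "Subject interview" as a safety assessment (Synopsis). Protocol 6.7 adds: "The subject may return to the investigational site for unscheduled visits during the study".

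**After healing.** Control visits stop. ACTitouch subjects are seen monthly for three months (Protocol 6.6).

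**The concern.** Three of the four components of the composite (infection, maceration, reaction to the dressing) are signs that an examiner can find on the limb. A sign that appears and clears between two ACTitouch visits would usually still be there at a weekly control visit. The tested quantity is the proportion of subjects ever recorded with an event, so more looks can yield more recorded events at the same true rate. Stratifying by ulcer size and duration does not touch this.

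This comparison is the stated safety objective (Protocol 12.2) of an open-label trial in which the device is expected to match bandaging on healing and gain on other grounds. A lower recorded rate of maceration or infection would be easy to read as a benefit of the device when part or all of it came from the visit schedule.

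**Working it through.** The documents give no adverse event rate, detection rate or safety power, so there is no planned figure to reproduce. The check asks how large the distortion could be.

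**Inputs from the documents**
- Control, open ulcer: 16 visits, every gap 1 week.
- ACTitouch, open ulcer: 7 visits, gaps 1, 1, 2, 2, 3, 3, 4 weeks (sum 16).
- 102 subjects per arm (Synopsis). The SAP table shells show 122 and 128.
- Two-sided alpha 0.05 (Protocol 12.1).

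**Assumptions**
- Onset uniform over 16 weeks, one episode per affected subject, sign visible for *d* weeks.
- True incidence 20% in both arms (10% and 30% as a range).
- All limbs unhealed to week 16.
- Unstratified normal approximation to the CMH test.

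**Step 1. Share found at visits** = Σ min(gap, *d*) / 16.

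| *d* (weeks) | Control | ACTitouch | Ratio |
|---|---|---|---|
| 0.5 | 8/16 = 50% | 3.5/16 = 21.9% | 0.44 |
| 1 | 16/16 = 100% | 7/16 = 43.8% | 0.44 |
| 2 | 100% | (1+1+2×5)/16 = 12/16 = 75% | 0.75 |
| 3 | 100% | (1+1+2+2+3+3+3)/16 = 15/16 = 93.8% | 0.94 |
| 4 or more | 100% | 16/16 = 100% | 1.00 |

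**Step 2. Chance of a significant result favouring ACTitouch** = Φ{[(p₁ − p₂) − 1.96·SE₀]/SE₁}, with SE₀ pooled and SE₁ unpooled. Without any detection difference it is 2.5%.
- *d* = 1: p₂ = 0.20 × 7/16 = 0.0875. (0.1125 − 1.96 × 0.0491)/0.0485 = 0.33, chance 63%.
- *d* = 2: p₂ = 0.20 × 12/16 = 0.15. (0.05 − 1.96 × 0.0532)/0.0531 = −1.02, chance 15%.
- At 10% and 30% incidence: 34% and 84% for *d* = 1; 9% and 23% for *d* = 2.
- With 122 and 128 subjects, at 20%: 72% for *d* = 1 and 18% for *d* = 2.

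**Step 3. Capture between visits.** Let contacts catch a share *s* of episodes missed at visits, and diary or recall at the next visit a share *r*. For *d* = 1 the ACTitouch share is 1 − (9/16)(1 − s)(1 − r).
- s = r = 0.5: 1 − 0.5625 × 0.25 = 0.859, so 20% v 17.2%, chance about 7%.
- s = r = 0.8: 1 − 0.5625 × 0.04 = 0.978, chance 3%.
- r = 1: ratio 1.00, no distortion.
- Perfect contacts, no recall, *d* = 0.5: ACTitouch has 7 visits and 11 contacts. These cover 18 × 0.5 = 9 weeks, less two overlaps of 0.071 week, so 8.86/16 = 55.4% against 50% in control. The ratio is 1.11 and the direction reverses.

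**Step 4. Healing before week 16.** Clinic visits by week 16, taking a month as 4.345 weeks, control v ACTitouch: healed at week 4, 4 v 5; week 6, 6 v 6; week 9, 9 v 6; week 12, 12 v 6. The imbalance in looks is absent or reversed for early healers and returns for later ones.

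**Step 5. Shared visits only.** Counting only events present at weeks 1, 2, 4, 6, 9, 12 and 16 gives the same detection share in each arm. For *d* = 1 that is 8.75% v 8.75%, and the chance of a false ACTitouch advantage returns to 2.5%.

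**The case against.** A reader might infer that, at equal true risk, ACTitouch will necessarily look safer. The documents do not support that. They give no episode duration or capture rate, and several provisions work against the bias: diary, interview, instructions to call, unscheduled visits with full procedures, and 11 contacts in the ACTitouch arm alone. ACTitouch subjects take the device off for bathing and can see the leg, whereas control limbs stay bandaged between visits. Reporting of limb infection and skin irritation (Protocol 9.3) is not confined to scheduled visits. The schedule of activities is not legible in the file, so event collection at the contacts cannot be excluded. After healing, only ACTitouch subjects continue to be seen. All of this stands. It makes the bias a possibility of uncertain size, and the 63% figure a worst case for 7-day episodes.

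Nor is the comparison wholly unadjusted: the CMH test is stratified, and hospitalization does not depend on examining the limb.

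A second tempting step is to replace the planned test by the shared-visit test. That could mislead too, because weekly care may shorten control episodes. Suppose episodes last 3 weeks if unseen and end about 7 days after detection. Shared visits would then show 15/16 = 94% in ACTitouch but only 7/16 to 12/16 (44% to 75%) in control, while the all-event test would show 94% v 100%. Real ACTitouch events found at unscheduled visits and resolved before the next scheduled one would also drop out. This objection stands, and it is why both tests are needed.

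None of it supplies what the plan lacks: any analysis in which both limbs are looked at equally often.

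**Conclusion.** The concern holds in a limited form. The 16 v 7 examination schedule for open ulcers and the absence of any allowance for it in Table 14.3.3 are facts of the documents. The consequence is a possible, not certain, bias towards ACTitouch for short-lived signs found on examination.

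Under the stated assumptions, the ratio of detected shares runs from 0.44 (signs lasting a week or less, visits only) to 1.00 (signs lasting 28 days or more, or fully reported). It can exceed 1 if the ACTitouch-only contacts detect very well. At 20% incidence and 102 per arm, the chance of a false significant advantage runs from about 63% (7 days, visits only) through 15% (14 days, visits only) and 7% (7 days, half caught by contacts and half by recall) to the nominal 2.5%. These figures treat every limb as unhealed and the outcome as wholly examination-dependent; early healing and the hospitalization component would weaken them. The plan should be changed because a recorded difference in favour of ACTitouch could not otherwise be interpreted.

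**What to change.** 1. Keep the all-event CMH comparison in Table 14.3.3.
2. Beside it, add a CMH comparison, with the same strata, of infection, maceration, allergic reaction and the composite, based on events present at weeks 1, 2, 4, 6, 9, 12 and 16 while the ulcer is open. Derive presence from the onset and stop dates already held for the listing in Table 16.2.7.1, and state how an event that stops on a visit day is counted. Include hospitalizations for worsening VLU from any source.
3. State that no safety advantage for ACTitouch will be concluded unless the shared-visit comparison supports it.

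Exposure-adjusted rates alone would not do, because they correct for time observed and not for the number of looks.

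**Cost.** SAP wording and a little programming, with no new data. The shared-visit comparison leaves out events in either arm, including those found at unscheduled visits, that resolve between shared visits, and it reflects any shortening of control episodes by weekly care. It must therefore be read together with the all-event result.

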8.3 Efficacy Analyses

All analyses will be carried out on the ITT population.

8.3.1 Primary Efficacy Analysis

The percentage of each subject's ulcer area reduction at 16 weeks will be assessed using a specialized ulcer camera and ulcer imaging system. Images will be centrally read by a qualified independent adjudicator. The percentage of ulcer area reduction for the ACTitouch® treated subjects will be compared with multi-layer bandaging treated subjects using a linear mixed model analysis of covariance (ANCOVA) with the following covariates: treatment group; duration of VLU ([1,6]; (6,24] months); baseline size of VLU, [1.5, 12cm], (12,50cm]; history of diabetes; age. The analysis will be conducted on the ITT population (Table 14.2.3).

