#### **5.0 Study Design:**

The study is a two arm, open label, non-inferiority, prospective, stratified, multi-center, RCT. As part of screening there will be a two week run in period measuring the VLU initial treatment response. The study is designed to evaluate percentage of ulcer area reduction in venous leg ulcer patients comparing ACTitouch to multi-layer bandaging during the 16 week treatment phase.

[figure not shown]

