  - Endovenous ablation or other venous surgery within two weeks of enrollment
    - Venous ultrasound must be completed after procedure to determine whether there is still venous insufficiency at the time of enrollment.
  - History of skin sensitivity to any of the components of AT, multi-layer bandages or compression garments.
  - History of an acute deep vein thrombosis (DVT) or pulmonary embolism (PE) within the last three (3) months.
  - Acute thrombophlebitis within the last six (6) weeks.
  - History of pulmonary edema or decompensated congestive heart failure within six (6) weeks of screening.
  - Currently has an active infection of the skin on the target limb such as cellulitis requiring antibiotics.
  - History of target limb cancer within the last two years with the exception of treated non-melanoma skin cancer unless ulcer biopsy performed at screening is negative for neoplasia.
  - Active cancer receiving chemotherapy and/or radiation therapy.
  - Poorly controlled diabetes with an HbA1c value of > 12% within the past three (3) months.
  - Changes to medications that affect edema within the last 30 days prior to enrollment (e.g. diuretics, calcium channel blockers of the dihydropyridine class, pioglitazone, cox-1 inhibitors, pregabalin, and gabapentin, diltiazem or fluctuating doses of systemic steroids).
  - Use of systemic corticosteroids requiring daily administration at doses greater than 5mg of Prednisone per day or equivalent for greater than two weeks.
    - Low dose steroid administration (Prednisone up to 5mg per day or equivalent) is allowable for an unlimited period of time. Topical steroid administration to peri-ulcer area or other skin is allowable but cannot be applied to the ulcer itself.
  - Currently pregnant or trying to become pregnant.
  - Inability or unwillingness to participate in all aspects of study protocol.
  - Exhibit any condition which, according to the Investigator, justifies the subject's exclusion from the study, such as a medical condition where an increase in venous or lymphatic return is undesirable.
  - Currently participating in another clinical trial.

5.2.3 Additional Exclusions after two week run-in: Subjects will exit the study if they meet any of the following criteria:

- Subject's target ulcer has decreased in size by greater than 30% compared to the baseline area.
- Subject's target ulcer has increased in size by greater than 50% compared to the baseline area.

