#### 12.6.2 Primary Endpoint Analysis:

The percentage of each subject's ulcer area reduction at 16 weeks will be assessed using a specialized ulcer camera and ulcer imaging system. Images will be centrally read by a qualified independent adjudicator. The percentage of ulcer area reduction for the ACTitouch® treated subjects will be compared with multi-layer bandaging treated subjects using analysis of covariance (ANOCOVA) with the following covariates: treatment group; duration of VLU ([1,6]; (6,24] months); baseline size of VLU, [1.5,12cm], (12,50cm]; history of diabetes; age. The analysis will be conducted on the ITT, MITT and Completer populations. The covariate adjusted one-sided lower bound 97.5% confidence interval of the treatment difference in mean percent ulcer area reduction (calculated as mean of ACTitouch® group minus mean of multi-layer bandaging treated group) is compared to the non-inferiority margin (-.125). If the lower bound exceeds the margin, the null hypothesis is rejected, and ACTitouch® system is deemed non-inferior to multi-layer bandaging.

A treatment-by-study center interaction will be assessed at the 0.10 level of significance using analysis of covariance with effects for treatment, study center and treatment-by-study center interaction. A non-significant interaction or any significant interaction deemed only quantitative in nature will not preclude study centers from being pooled for the final analysis. A significant qualitative interaction will be further inspected to

assess the study centers causing the interaction. Study centers with less than 15 subjects will be pooled by geographic region prior to carrying out the analysis.

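### The primary model uses ulcer size only as two classes and leaves out the run-in area change: a valid model, but a missed gain in precision from data collected before randomization

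*SAP*

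**What the plan says.** Protocol 12.6.2 lists the terms of the primary model as "treatment group; duration of VLU ([1,6]; (6,24] months); baseline size of VLU, [1.5,12cm], (12,50cm]; history of diabetes; age". SAP 8.3.1 repeats the list, with size again given as "baseline size of VLU, [1.5, 12cm], (12,50cm", and so does the note to SAP Table 14.2.3. The size and duration cut-points are those used to stratify randomization (protocol 12.1).

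The same covariates carry over to the multiple imputation model (protocol 12.6.2), the Charing Cross analysis (protocol 12.6.3, SAP 8.3.2), the exploratory models (protocol 12.6.4, SAP 8.3.3) and the interim comparison (protocol 12.7).

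The finer data are collected. Protocol 5.0 states that "there will be a two week run in period measuring the VLU initial treatment response", and protocol 5.3 puts every subject on multi-layer bandaging during that time. Under protocol 7.9, at each study visit "the wound will be traced using the Silhouette™ system". The run-in change has one stated use, as an exit rule in protocol 5.2.3. A subject leaves if the "target ulcer has decreased in size by greater than 30% compared to the baseline area", or if the "target ulcer has increased in size by greater than 50% compared to the baseline area".

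**The concern.** Non-inferiority is declared when the lower confidence bound for the difference in mean percent area reduction lies above -0.125. The width of that interval therefore bears directly on the result.

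The two-class size term gives a 1.5 cm² and a 12 cm² ulcer the same adjustment, and likewise a 13 cm² and a 50 cm² ulcer. The run-in supplies each subject's own change in area on standard bandaging just before randomization. The protocol treats that change as informative enough to decide who may be randomized, then makes no use of it among those who are.

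If either measure predicts week-16 reduction beyond the terms already listed, the residual variance is larger than it need be, and the interval is wider.

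**Working it through.** **1. Inputs.** From the documents: 102 per arm (protocol Synopsis), margin 0.125 and one-sided alpha 0.025 (protocol 12.6.1 and 12.6.2). The final alpha of 0.0249 in protocol 12.7 changes the implied SDs below by 0.0002 or less. No text is shown under protocol 12.4, so the SD, planned power and dropout allowance are unavailable and 204 cannot be reproduced independently. Assumed here: true difference 0 (also the value protocol 12.7 sets for conditional power), power 80% or 90%, no dropout.

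**2. SD implied by 102 per arm.** SD = 0.125 / [(z₀.₉₇₅ + z_power) × √(2/102)], with √(2/102) = 0.1400.
- 80% power: 0.125 / (2.8016 × 0.1400) = 0.3186
- 90% power: 0.125 / (3.2415 × 0.1400) = 0.2754

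With a 20% dropout allowance, the implied SDs would be 0.285 and 0.246.

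**3. Effect of an added partial R².** This is the share of the remaining variance explained beyond the listed covariates. The residual SD becomes SD × √(1 − R²), power is Φ[0.125 / (SD_res × 0.1400) − 1.960], the 95% half-width is 1.960 × SD_res × 0.1400, and the number per arm for unchanged power is 102 × (1 − R²), rounded up.

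| Added partial R² | Power, from 80% | Half-width, from 80% | Per arm for the same power | Power, from 90% |
|---|---|---|---|---|
| 0 | 80.0% | 0.0874 | 102 | 90.0% |
| 0.02 | 80.8% | 0.0866 | 100 | 90.6% |
| 0.05 | 82.0% | 0.0852 | 97 | 91.4% |
| 0.10 | 84.0% | 0.0830 | 92 | 92.7% |
| 0.20 | 88.0% | 0.0782 | 82 | 95.2% |

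The relative narrowing does not depend on the SD or the sample size. It is 1 − √0.98 = 1% at the low end and 1 − √0.80 = 11% at the high end. It therefore applies equally if the 122 and 128 in the SAP table shells are the actual numbers.

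**4. What the cut at 12 keeps of log area.** This depends on the size distribution, which the documents do not give.
- Assumed lognormal areas restricted to 1.5–50 cm² (median 4 to 12, log SD 0.8 to 1.2): simulation gives 39% to 69% of the variance of log area retained.
- Assumed log-uniform areas: the lower class holds p = ln(12/1.5) / ln(50/1.5) = 2.079/3.507 = 0.593, and the share kept is 3p(1 − p) = 72%.

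**5. What the run-in limits leave.** Subjects who remain have area ratios from 0.70 to 1.50, that is, log ratios from −0.357 to 0.405. Simulation with a log-ratio SD of 0.2 to 0.5 shows that a correlation of 0.3 to 0.5 in the unrestricted population (R² 0.09 to 0.25) becomes an R² of about 0.02 to 0.20 among those randomized. That is the source of the range in step 3. It is a simple R², so the partial value beyond duration, size class, diabetes and age could be lower.

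**The case against.** **The model is sound as written.** It is given identically in both documents and contains both stratification factors. A reader might infer that leaving out continuous area or run-in change biases the comparison or invalidates the test. It does not: randomization protects the comparison, and the confidence interval already allows for residual chance imbalance. This objection stands, and it is why the point is only about efficiency.

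**The gain may be small.** This also stands. The outcome is a percent reduction, already scaled to each subject's own ulcer, so an eightfold range of area within a class does not by itself show lost prognostic information. Healing caps the outcome at 100%, which can weaken linear covariate effects. The run-in limits restrict the second covariate. The two covariates are also linked, because area at the Randomization Visit equals starting area times the run-in ratio, so their separate contributions cannot simply be added.

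**Stronger figures are tempting.** A reader might apply the familiar 64% (2/π) as a ceiling on what two classes retain. That value is for a median split of a normal variable, and step 4 shows that other distributions fall on either side of it. A reader might also call the run-in response the best predictor of week-16 reduction. The documents contain nothing to support that.

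**The mixed model may seem to cover it.** SAP 8.3.1 names a linear mixed model, from which a reader might infer that the run-in measurements already enter. The section names no repeated visits and no random effect, and its covariate list has no run-in term.

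**Timing.** The SAP carries the date 8 October 2017 and its shells already show 122 and 128 subjects. Changing the primary model late in an open-label trial has a cost in credibility. This governs how the change is made and labelled, but does not remove the point.

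**Conclusion.** The point holds as a missed gain in precision of low severity. Ulcer size enters only as two classes, and the run-in area change is absent from the primary model and from every analysis that borrows its covariates, although both are available before randomization on a continuous scale.

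The direction is secure: prespecified adjustment for pre-randomization measures does not bias the comparison, and it narrows the interval to the extent that they predict the outcome. The size is not secure. On the stated assumptions the range is about 1 to 8 power points from an 80% base, or 2 to 20 fewer subjects per arm for the same power. A figure near the bottom of that range is plausible, and no single value should be quoted as the gain. The documents do not support saying that the trial is underpowered because of this choice.

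**What to change.** - Keep both stratification factors in the model.
- Add log ulcer area at the Randomization Visit and the log ratio of that area to the area at the start of the run-in, both continuous.
- Carry the same terms into the imputation model, the interim model and the secondary and exploratory analyses that reuse the list.
- State which visit is baseline for the outcome. The run-in rule in protocol 5.2.3 measures against an earlier baseline area, while the size strata begin at 1.5, the Randomization Visit minimum. If the outcome is measured from the start of the run-in, the run-in change is part of it. If it is measured from the Randomization Visit, measurement error in that area is shared by covariate and outcome. Both covariates precede randomization either way, but the choice affects how they relate to the outcome.
- Say whether the site or the adjudicated tracing supplies each area. Protocol 7.9 lists the initial, enrollment and healed visits for adjudication and does not name the Randomization Visit.
- Fix this before any unblinded comparison is seen, including the interim. If that moment has passed, keep the listed model as primary and report the extended one as a prespecified sensitivity analysis, labelled as such.

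The cost is two degrees of freedom and consistent wording across the primary, interim and imputation models. No new data or visits are needed.
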